7.0 Statistical Considerations

Descriptive statistics will be performed for all continuous variables (mean \pm standard deviation for normally distributed variables and median \pm interquartile range for non-normal variables) and categorical variables (count and proportion). Categorical outcomes will be analyzed using χ^2 test or Fisher's test for small samples. Comparison of group outcomes will be analyzed using Student's t test for normally distributed data and nonparametric Wilcoxon-Mann-Whitney test for data that violate the normality assumption. Univariate logistic regression analysis will be used to identify predictors of interest and multiple predictor analysis will estimate effects adjusted for covariates.

Diagnostic test characteristics including sensitivity, specificity, positive predictive value, negative predictive value, and accuracy will be assessed for the UTDT in diagnosing PEP and for different severity levels of PEP. In addition, the UTDT will be assessed in predicting additional outcomes as outlined above.

Specific pre-procedure, intra-procedure, or post-procedure characteristics as noted above will be assessed in univariate and multivariable regression models to assess whether they contribute to the inaccurate diagnosis of PEP based on the UTDT. Similar multivariable regression analysis will be done to assess for additional risk factors of PEP.

A cost analysis will also be performed to determine the number of UTDT strips needed to prevent one inadvertent discharge of a patient with PEP.

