1.0 Background

Post-endoscopic retrograde cholangiopancreatography (ERCP) pancreatitis (PEP) is the most common, serious complication of ERCP and accounts for a significant proportion of morbidity, mortality, and health care expenditures accrued in the post procedure setting.³⁻⁵ Large studies have shown that PEP occurs approximately 4-10% procedures with a mortality rate up to 0.7%.⁶⁻⁸

ERCP is most often performed in the outpatient setting with the expectation for patients to be discharged home the same day of the procedure. Patients are often observed for symptoms of complications after procedures. Data suggests prolonged observation (4-6 hours) captures symptoms indicative of a complication in 80% of these patients and consequently prevents un-intended discharge with subsequent hospitalizations.⁹ However, a standardized observation protocol for this interval of time is not practical at ERCP centers. Given 11% of patients require admission after ERCP and fewer patients ultimately are verified as having complications; the majority of centers do not have a 4-6 hour observation protocol for post-ERCP care. Moreover, such a protocol for all ERCP outpatients would create unnecessary costs, strain on recovery room resources (staff, nursing and space), and significant inconvenience for patients.¹⁰ While several factors including peri-procedural pain, history of pancreatitis, and performance of sphincterotomy predict need for hospital admission after ERCP, no single clinical factor has proven accuracy. Complex models for predicting admission are cumbersome and struggle to achieve a AUC ROC beyond 0.90 for predicting need for admission, much less post ERCP pancreatitis.¹¹ However, while same-day discharge after ERCP is widely utilized and relatively safe, it has been associated with readmissions.⁹ We have reported rates of inadvertent discharge and readmission of outpatients with post ERCP pancreatitis to occur in up 25%.¹² A recent review of patients enrolled in a prospective study, at risk for post ERCP pancreatitis demonstrated that rate of inappropriate discharge may occur in over 50% of patients. This delay in recognition may be clinically important as this represents a missed opportunity for timely interventions. For instance, early intravenous fluid hydration after the development of pancreatitis can reduce the morbidity and mortality at least 3-fold.^{12,13}

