2.0 Rationale and Specific Aims

Post-endoscopic retrograde cholangiopancreatography (ERCP) pancreatitis (PEP) is the most common, serious complication of ERCP. More than 500,000 ERCP procedures are performed from which 25,000 cases of PEP occur in the U.S.A. annually. PEP accounts for significant morbidity and health care expenditures. While symptoms of PEP arise immediately after ERCP, they are non-specific. Consequently, unnecessary admissions of outpatients without PEP and inadvertent discharge of outpatients with PEP from ERCP recovery are common. An accurate, confirmatory test for diagnosis of PEP immediately after ERCP is lacking. Urine Trypsinogen-2 Dipstick test (UTDT) is a simple, inexpensive test with promising preliminary data for accuracy for immediate diagnosis of PEP. Prior studies of UTDT test characteristics lack rigorous scientific design.

Proposed Study and Methods:

We will enroll 1825 ERCP outpatients at our institution in a prospective cohort study. A pre-ERCP UTDT test and diagnostic UTDT 2 hours after the ERCP will be performed. Patients with a positive baseline UTDT will be followed clinically as part of this study without 2 hour testing. Care providers and study primary investigators will be blinded to the 2 hour UTDT results. Baseline, intra-procedure and recovery room clinical data will be recorded. Diagnosis of PEP will be made blinded to the UTDT result. Admission status for PEP will be assessed by review of records and phone/e-mail contact 5 days and 30 days after ERCP procedure. Sensitivity and specificity of 2 hour post ERCP UTDT for the diagnosis of PEP will be calculated.

Aims: 1) To determine the test characteristics of UTDT for the diagnosis of PEP 2 hours after completion of ERCP. 2) To identify and describe patients with baseline UTDT positivity, in whom this test offers limited utility.

Specific Aims:

Primary Aim

1.1 To determine the test characteristics (sensitivity and specificity) of the UTDT for the diagnosis of PEP:

Hypotheses:

- 1) UTDT is a sensitive and specific test for the diagnosis of PEP for patients undergoing ERCP.
- 2) At a cutpoint for a negative test of <50ug/L, UTDT will be accurate at 2 hours post ERCP in patients whose baseline test is negative.

Secondary AIM:**1.1 To identify and describe patients with baseline UTDT positivity.****Hypothesis:**

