1) A subgroup of patients will demonstrate baseline positivity for UTDT. Based on previous studies, the subgroup is likely to include patients with chronic inflammatory or obstructive conditions of the pancreatic duct (pancreatic ductal adenocarcinoma, obstructive chronic pancreatitis)¹ This subgroup will represent a minority (<6%) of outpatients presenting for ERCP.¹

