5.0 Study Procedures

Informed Consent: Eligible patients will sign an IRB-approved, written informed consent to verify their willingness to participate in this study. Informed consent will be obtained on the day of their scheduled ERCP. Consent for the study will be obtained by one of the participating endoscopists and/or a research assistant. Patients will receive a copy of the signed and dated informed consent document. Original informed consent documents will be maintained on-file. A note may be made in the subject's medical record regarding participation in the research study. Once consented and enrolled into the trial, patients will be issued a unique identifier for the purposes of data entry.

Pre-Procedure data and sample collection: After obtaining informed consent, patients will be asked health questions prior to ERCP to assess and quantify current and prior alcohol use, current and prior tobacco use, quantification of narcotic use and quantification of non-steroidal anti-inflammatory drug (NSAID) use. Narcotic and NSAID use in the 7 days prior to ERCP will be recorded. Abdominal pain scores will be collected at baseline and post ERCP. Subjects will be shown the study pain scale (appendix 1) and asked to pick a number on the scale to rate their abdominal pain at baseline and post ERCP. Amount and type of IV fluids given Pre-ERCP may be collected. Post- ERCP Pain scores will be attempted 2 -3 hours Post –ERCP, but if necessary may be collected prior to the 2 hours Post –ERCP time point up to the time of patient discharge by the study research technician.

Data will be collected on the indication of ERCP, history of acute pancreatitis, recurrent acute pancreatitis, or chronic pancreatitis, history of pancreatic surgery, presence of peri-pancreatic fluid collection and prior sphincterotomy. Data will also be collected to note if subjects underwent an endoscopic ultrasound with fine needle aspirate during the same visit as baseline ERCP. Prior imaging may be reviewed for the presence of pancreatic mass and/or pancreatic duct obstruction.

Baseline tests may be obtained prior to undergoing ERCP including serum pancreatic enzymes (amylase, lipase), serum liver enzymes, and coagulation profile, as is the standard for our endoscopy unit. Available outpatient laboratory data within 48-72 hours of ERCP will be reviewed. If Pre- ERCP baseline lab

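### The PEP risk-factor model relies on univariate selection from 30 to 44 recorded variables and does not exclude post-procedure ones, so chance findings are likely and circular ones possible

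*Combined protocol and SAP*

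**What the plan says.** Three sentences in Section 7.0 of the combined protocol and SAP govern these models.

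- General method: "Univariate logistic regression analysis will be used to identify predictors of interest and multiple predictor analysis will estimate effects adjusted for covariates". The sentence names no outcome and gives no entry threshold.
- UTDT-inaccuracy model: "Specific pre-procedure, intra-procedure, or post-procedure characteristics as noted above will be assessed in univariate and multivariable regression models". The stated purpose is to see whether these characteristics explain wrong UTDT results.
- PEP model: "Similar multivariable regression analysis will be done to assess for additional risk factors of PEP". It has no covariate list of its own.

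Section 7.0 gives no multiplicity rule, limit on model size, penalisation or internal validation.

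The characteristics referred to are those recorded in Section 5.0. One group is "history of acute pancreatitis, recurrent acute pancreatitis, or chronic pancreatitis, history of pancreatic surgery, presence of peri-pancreatic fluid collection and prior sphincterotomy". Others are alcohol, tobacco and drug use, laboratory values, stents, cannulation manoeuvres and procedure duration. After the procedure, the study records pain score, nausea or vomiting, anti-emetics, narcotics given for pain, fluids, time in recovery and the decision to admit or discharge.

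**The concern.** Two separate problems follow if the text is applied as it stands.

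**Selection.** Choosing predictors by univariate tests keeps chance associations and can drop true predictors that are masked by confounding. The p-values and confidence intervals of the second-stage model take no account of the selection. This matters more when events are few relative to candidates.

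**Circularity.** Several post-procedure variables are symptoms of PEP, responses to it, or part of how it is ascertained. If they enter a risk-factor model, the outcome is regressed partly on its own components. Effects of upstream factors, such as stenting or cannulation technique, may be attenuated because the model conditions on something that lies downstream of PEP.

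At stake is the credibility of a reported list of PEP risk factors. The diagnostic accuracy results are not at stake.

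**Working it through.** **Inputs**

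- Enrolment, Section 2.0: "We will enroll 1825 ERCP outpatients at our institution in a prospective cohort study".
- PEP rate, Section 1.0: "PEP occurs approximately 4-10% procedures".
- PEP rate, Section 2.0: "More than 500,000 ERCP procedures are performed from which 25,000 cases of PEP occur in the U.S.A. annually". This implies 25,000/500,000 = 5%, or slightly less because the denominator is a minimum.
- Candidates, counted from Section 5.0: 23 pre-procedure, 12 intra-procedure and 9 post-procedure, so 44 in all and 35 without the post-procedure ones. The count depends on how grouped items are split (for example, amount and type of fluid), so 30 serves as a conservative lower figure.
- Not in the documents, assumed here: two-sided 0.05, screening at p<0.05 (p<0.20 as a variant), and 10 events per parameter as a rough guide.

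The documents give no derivation of 1825 and no expected PEP count, so there is no planned figure to reproduce.

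**Expected events = 1825 x rate; events per candidate = events / k**

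| PEP rate | Events | k = 30 | k = 35 | k = 44 |
|---|---|---|---|---|
| 4% | 73 | 2.4 | 2.1 | 1.7 |
| 5% | 91 | 3.0 | 2.6 | 2.1 |
| 10% | 183 | 6.1 | 5.2 | 4.1 |

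All 1825 is the natural denominator. Section 5.0 has baseline-positive patients undergo everything except the 2-hour test, so their PEP outcome is known. Section 2.0 says of them: "This subgroup will represent a minority (<6%) of outpatients presenting for ERCP". Leaving out 6% would give 69, 86 and 172 events, which changes nothing material. The documents do not say whether 1825 is counted before or after screen failures; if before, events would be fewer.

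**Chance findings, all k candidates null and independent**

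Expected false predictors = 0.05k. Chance of at least one = 1 - 0.95^k.

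- k = 30: 1.5 expected; 1 - 0.95^30 = 78.5%.
- k = 35: 1.75 expected; 83.4%.
- k = 44: 2.2 expected; 89.5%.

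These figures do not depend on the event count.

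**Does the multivariable step remove them?** A null simulation used 300 runs per setting, 1,716 patients, independent binary candidates each present in 30%, and PEP at 4%, 5% and 10%. It screened at p<0.05 or p<0.20 and then fitted a multivariable logistic model. At least one false factor remained at p<0.05 in 74-79% of runs (30 candidates), 79-85% (35) and 86-90% (44). The second step gives little protection.

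**Circularity, by comparing sections**

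- Section 1.0 makes characteristic abdominal pain one of three criteria, of which two define PEP. Section 5.0 records recovery pain and the narcotics given for it.
- Section 5.0 classifies patients who were not hospitalised for attributable symptoms as free of PEP. It also records the recovery-room admission decision. That decision is not identical to the outcome, since a discharged patient can be readmitted with PEP, but it is closely tied to it.

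**Model size at 10 events per parameter:** 73/10, 91/10 and 183/10 support about 7, 9 and 18 parameters at 4%, 5% and 10%.

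**The case against.** The strongest reply is that the plan does not say what a quick reading suggests.

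- A reader might infer that post-procedure variables are expressly planned for the PEP model. They are not. They are named for the UTDT-inaccuracy model, where recovery factors such as fluid volume are reasonable candidates. They reach the PEP model only through the word 'Similar', which may refer to method alone, and the term 'risk factors' does not naturally cover consequences of PEP. This stands: it is an ambiguity to close, not a stated plan.
- A reader might infer that only about 70 events will be available. That figure needs the lowest rate in the documents; their own 5% gives about 91 and the top of the range about 183. This also stands, although events per candidate stay below 10 throughout.
- The selection rule is loosely worded. There is no threshold, and no rule that only univariately significant variables go forward. 'Specific' characteristics may mean a subset. This is fair, but the sentence still gives univariate regression the job of identifying predictors, and no subset is named.
- The 79-90% assumes independent candidates that are all null. Many recorded items, such as the pancreatitis histories, are plausibly correlated, and some are probably real predictors. The percentages illustrate the risk and do not forecast it.
- PEP risk factors are neither the primary nor the secondary aim. This is correct and limits the importance of the point.

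**Conclusion.** The point holds as a minor, inexpensive improvement to an exploratory analysis. With about 73 to 183 expected PEP events and 30 to 44 candidates, univariate selection without a prespecified list is likely to produce at least one chance predictor: 79% to 90% under an assumed p<0.05 screen of independent null candidates. Circular findings and attenuated upstream effects are possible, and only if post-procedure variables are entered, which the text allows but does not require. The documents do not support a claim that spurious or reverse-causal factors will certainly appear, and no calculation here sizes the attenuation. The primary estimates of sensitivity and specificity are untouched.

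**What to change.** Amend Section 7.0 before data lock as follows.

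1. State that the PEP risk-factor model uses only pre- and intra-procedure variables. Post-procedure variables may stay in the UTDT-inaccuracy model.
2. Replace univariate selection with a named covariate list sized to the expected events: about 7 parameters at 4% PEP, 9 at 5% or 18 at 10%, if 10 events per parameter is accepted as a guide. Count every category of a multi-level variable as a parameter.
3. Fit that model once. Penalisation is optional; the list and the exclusion matter more than the choice of penalty.
4. Report univariate results as descriptive and label the risk-factor analysis exploratory.

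The cost is a wording change and agreement on the list. No new data or patients are needed. The downside is that variables left off the list get descriptive results only.

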Actim Pancreatitis (Medix Biochemica) is a urine trypsinogen-2 dipstick test (UTDT) that uses trypsinogen-2 as a biomarker for acute pancreatitis. At a cutpoint of 50 ug/L it has been assessed in 3 small prospective studies for the diagnosis of PEP.^{1,25,26} Kemppainen et al.²⁵ demonstrated an adequate sensitivity (81%) and specificity (97%) with the UTDT for diagnosing PEP at 6 hours after ERCP in 106 patients. Limitations include the impracticality of a 6 hour testing interval after ERCP and unclear inclusion/exclusion criteria. Sankaralingam et al.²⁶ demonstrated a very high sensitivity (100%) and specificity (96%) with the UTDT for diagnosing PEP at 4 hours after ERCP, but was limited by the small sample size of 29 patients. Tseng et al.¹ demonstrated a sensitivity of 85%, specificity of 97%, and a superior accuracy of 96% compared to serum amylase/lipase for the diagnosis of PEP at 3 hours after ERCP in 150 patients, but limitations include a high number (100) of excluded patients. A meta-analysis of these available studies calculated an overall sensitivity of 86%, specificity of 94% and area under the operator curve of 0.92.²⁷ However, as mentioned above, the published studies suffer from variation in timing of UTDT, inclusion/exclusion criteria, and lack of rigorous study design with adequately powered sampled size. Consequently, further study is needed to assess its accuracy of UTDT in the post ERCP setting.

The primary study objective is to determine the test characteristics of UTDT for the diagnosis of PEP 2 hours post ERCP.

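### The regression on inaccurate UTDT diagnosis does not separate false negatives from false positives; read literally, a true odds ratio of 3 for missed PEP would appear as about 1.1–1.5

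*Combined protocol and SAP*

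**What the plan says.** Section 7.0 takes pre-, intra- and post-procedure characteristics into univariate and multivariable regressions to "assess whether they contribute to the inaccurate diagnosis of PEP based on the UTDT". It does not define that outcome or name the patients in whom it is modelled, and no other section does.

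Three neighbouring statements matter:

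- Section 7.0 plans a separate regression with PEP itself as the outcome: "Similar multivariable regression analysis will be done to assess for additional risk factors of PEP".
- Section 7.0 lists sensitivity, specificity, predictive values and accuracy, both for PEP overall and by PEP severity. It also plans a cost analysis of the strips needed to avoid one inadvertent discharge of a patient with PEP.
- Section 2.0 treats both kinds of mistake as clinically relevant: "unnecessary admissions of outpatients without PEP and inadvertent discharge of outpatients with PEP from ERCP recovery are common".

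On timing, Section 2.0 says "A pre-ERCP UTDT test and diagnostic UTDT 2 hours after the ERCP will be performed". Patients positive at baseline get no 2-hour test.

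**The concern.** A false negative can occur only in a patient with PEP, and a false positive only in a patient without it. If the outcome is coded as wrong versus right in everyone tested, the model mixes two error rates from two separate groups. Two things follow.

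1. **Dilution.** PEP is uncommon, so most errors are likely to be false positives. A factor that acts only on missed PEP is swamped by them.
2. **Artefact.** The error rate is 1 − sensitivity in cases and 1 − specificity in non-cases. When these differ, a factor that only makes PEP more likely, with test accuracy constant, shifts the overall error rate and looks like a cause of test error.

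What is at stake is the answer to which patients with PEP test negative. That is the error linked to inadvertent discharge.

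**Working it through.** The plan gives no figure for this regression, so there is none to reproduce.

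**Inputs from the plan**

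- Tested patients: 1,825 enrolled, with under 6% expected to be baseline positive and so not tested at 2 hours (Section 2.0). N = 1,825 × 0.94 ≈ 1,715, assuming no other loss.
- PEP rate p: 4–10% (Section 1.0), and 25,000/500,000 = 5% (Section 2.0).
- Sensitivity/specificity (Se/Sp) from Section 1.0: 86/94 (meta-analysis), 85/97 (3 hours) and 81/97 (6 hours). The 29-patient study with 100% sensitivity is left out because it implies no false negatives.

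**Assumptions**

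- These accuracies hold at 2 hours. The plan gives no 2-hour figure and itself notes that "the published studies suffer from variation in timing of UTDT".
- An illustrative binary factor is present in 20% of patients and has an odds ratio of 3.

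**Step 1: expected errors.** FN = N·p·(1 − Se); FP = N·(1 − p)·(1 − Sp).

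- 86/94 at 4% PEP: FN = 1,715 × 0.04 × 0.14 = 9.6; FP = 1,715 × 0.96 × 0.06 = 98.8; FP share 91%.
- 81/97 at 10% PEP: FN = 1,715 × 0.10 × 0.19 = 32.6; FP = 1,715 × 0.90 × 0.03 = 46.3; FP share 59%.

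Over all settings there are 10–33 false negatives and 46–99 false positives. The false-positive share is 79–91% at 4% PEP, 75–89% at 5% and 59–79% at 10%.

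**Step 2: pooled odds ratio.** The error probability in factor group x is e_x = p_x·FN_x + (1 − p_x)·FP_x, and the pooled OR is odds(e_1)/odds(e_0). The group rates are solved so that the overall rates stay at the cited values.

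*Factor acting on false negatives only, 86/94, 5% PEP.* False-negative rates of 0.1083 and 0.2670 have odds ratio 3 and average 0.8 × 0.1083 + 0.2 × 0.2670 = 0.14.

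- e_0 = 0.05 × 0.1083 + 0.95 × 0.06 = 0.0624
- e_1 = 0.05 × 0.2670 + 0.95 × 0.06 = 0.0703 (0.07035 before rounding)
- Pooled OR = 0.0757/0.0666 = 1.14

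*Factor acting on PEP risk only, 81/97, 10% PEP.* PEP rates of 0.0757 and 0.1972 have odds ratio 3.

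- e_0 = 0.0757 × 0.19 + 0.9243 × 0.03 = 0.0421
- e_1 = 0.1972 × 0.19 + 0.8028 × 0.03 = 0.0616
- Pooled OR = 1.49

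**Step 3: all settings.** Ranges run over the three accuracy pairs. Power is two-sided 5% Wald from expected 2×2 counts.

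| Factor triples the odds of | 4% PEP | 5% PEP | 10% PEP |
|---|---|---|---|
| False negative only: pooled OR | 1.11–1.24 | 1.14–1.29 | 1.27–1.50 |
| – power, pooled | 7–11% | 8–14% | 18–34% |
| – power, PEP cases only | 31–37% | 37–44% | 64–72% |
| PEP only: pooled OR (power) | 1.07–1.26 (6–12%) | 1.09–1.31 (6–15%) | 1.16–1.49 (10–33%) |
| False positive only: pooled OR | 2.5–2.8 | 2.4–2.7 | 2.0–2.5 |
| Both errors: pooled OR | 2.9–3.0 | 2.9–3.0 | 2.8–3.0 |

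Pooled power for the false-positive-only factor is 82–100%. The Wald approximation is rough at 10–12 events. A Fisher-test simulation of the false-negative-only rows (4,000 cohorts per setting) gave 29–32%, 34–39% and 59–66% in PEP cases only, and 6–11%, 8–13% and 17–32% pooled.

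**Step 4: sensitivity to the assumptions.**

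- *Lower 2-hour sensitivity.* At 97% specificity and 10% PEP, false positives become the minority once sensitivity falls below 1 − 0.90 × 0.03/0.10 = 73%. At an assumed 70/97 and 10% PEP their share is 47%, yet the false-negative-only factor still shows a pooled OR of 1.52 (power 43%, against 80% in PEP cases only).
- *Factor prevalence.* From 10% to 40%, at 86/94 and 5% PEP, the pooled OR for that factor is 1.15 to 1.12.

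**The case against.** The strongest reply is that Section 7.0 is silent here, not wrong. It speaks of models in the plural and never says that the two errors will be combined. A reader might infer that the plan commits to a pooled outcome. The text does not say that, and every figure above depends on the literal reading. This stands, and it makes the point a request to specify.

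Three further objections have force:

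- **Severity.** Sensitivity by PEP severity is already planned. That is the false-negative rate within cases, split by an obvious clinical feature, so missed cases would not go undescribed. It does not cover the other patient and procedure characteristics that the regression is meant to examine.
- **False positives.** A pooled model keeps most of the signal for the majority error, and Section 2.0 names unnecessary admission as a harm too. The odds ratio of 1.1–1.5 applies only to a factor acting on false negatives alone.
- **Gain in power.** At 4–5% PEP both approaches would usually miss a true odds ratio of 3. Splitting removes the dilution and the artefact, but not the scarcity of false negatives.

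The separate PEP risk-factor regression would help a reader recognise the artefact. It has a different outcome and cannot show which PEP cases are missed.

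**Conclusion.** The concern holds in a limited form. Read literally, the regression on inaccurate diagnosis would mostly describe false positives (59–91% of errors). It would show a threefold effect on missed PEP as an odds ratio of about 1.1–1.5, with power of 7–34% against about 31–72% in PEP cases alone. It would also give a factor that only triples PEP odds an apparent effect on test error: 1.07–1.31 at 4–5% PEP, where power is 6–15% against a nominal 5%, and up to 1.49 at 10%. Effects on false positives alone (about 2.0–2.8) or on both errors in the same direction (about 2.8–3.0) are largely preserved.

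The false-positive majority depends on accuracies measured at 3–6 hours or at mixed times and may not hold at 2 hours. The dilution persisted at the lower sensitivity tried.

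Two stronger readings are not supported. A reader might infer that the trial's accuracy results are compromised; they are not, because sensitivity and specificity are estimated separately from this regression. A reader might also infer that opposite effects on the two errors would cancel; that is possible in principle, but the documents identify no factor shown to act that way.

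Severity: COULD, a cheap improvement to a secondary analysis.

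**What to change.** Add to Section 7.0: *The 2-hour UTDT result will be modelled separately in patients with PEP (factors associated with false-negative results) and in patients without PEP (factors associated with false-positive results). The model in patients with PEP is exploratory.*

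Keep the PEP-case model to one or two prespecified factors, or fit it with Firth penalisation; either is a matter of judgement. The multivariable model can stay in non-cases, where 46–99 expected events would carry about 4–9 parameters at ten events each (a rule of thumb).

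The cost is one or two sentences and one extra model, with no new variable, visit or sample. The downside is imprecision. At 86/94, a true odds ratio of 3 in PEP cases has an expected 95% confidence interval of about 0.7–13 at 4% PEP, 0.8–11 at 5% and 1.2–7.6 at 10%. The report should give these intervals and should not read a non-significant result as no effect.
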